1. STUDY AIM, BACKGROUND, AND DESIGN ABSTRACT

The purpose of this study is to examine the effect of utilizing blood flow restriction (BFR) therapy in patients treated both non operatively and operatively for rotator cuff tears (RCT). BFR has been proposed to work by restricting arterial inflow leading to an oxygen depleted environment and the ability to induce muscle adaptation at lower maximum repetition via reactive hyperemia. Muscle atrophy occurs following rotator cuff tear. Thus, physical therapy is used to regain strength with the ultimate goal of returning to activity.

The goal of this investigation is to determine if using BFR during therapy for non-operatively managed and operatively managed rotator cuff tears would lead to increased and expedited strength gains. Additionally, the investigators would like to determine if BFR is beneficial in preventing muscle atrophy and fatty infiltration often seen in the setting of rotator cuff tear, as it is known that cuff tears can subject the muscles to degenerative changes and these patients are at risk for poorer clinical outcomes. The investigators will also look at patient reported outcomes metrics and pain scores to determine if BFR has a significant impact on the patient experience surrounding rotator cuff tear after both nonoperative treatment with therapy and operative treatment with surgical repair and peri-operative rehabilitation.

The investigators hypothesize that the BFR group will have significantly greater strength gains at all time points. Previous studies have shown that BFR has potential in increasing muscle torque generation and cross-sectional area in the first six months following anterior cruciate ligament (ACL) reconstruction. While there have not been as many studies investigating the use of BFR following upper extremity surgery, previous research has demonstrate that BFR can be useful both proximal and distal to the targeted muscle groups in the upper extremity. In addition to the paucity of research on post-operative BFR following rotator cuff repair (RCR), there is no evidence on pre-operative use as well. The investigators believe that the use of BFR in the perioperative period surrounding rotator cuff tear and repair has the potential to significantly decrease muscle atrophy and lead to faster, more substantial strength gains and less muscle atrophy and fatty infiltration.

2. SUBJECT POPULATION AND ELIGIBILITY

Subject Population

- Subjects will be recruited from our ambulatory sports medicine clinics. We will include patients aged 18-60 who suffered a rotator cuff tear and are undergoing Rotator Cuff reconstruction.
- Subjects will be excluded if they are undergoing revision RCR reconstruction, history of DVT, neurovascular injury, unable to tolerate BFR treatment, unable to complete physical therapy and peripheral vascular disease

Enrollment and/or Screening

- Subjects will be identified when they present to our ambulatory clinics with RCR tears. We will not access the medical record prior to presentation to our clinics. At the presentation we will discuss the project with potential subjects and if they express interest, we will then delve further into the chart to ensure they do not meet any exclusion criteria. Additionally, we will discuss exclusion criteria with the patient during a detailed history. We will develop a series of questions to screen for exclusion criteria, particularly relating to the history or family history of DVT.

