3. STUDY PROCEDURES

- Patients who are seen in clinic for rotator cuff pathology will undergo treatment for their rotator cuff based

on a shared decision-making process with the orthopedic surgeon, irrespective of this study. Once a treatment plan is in place, the patient will be introduced to this study and presented with the opportunity to participate. If the patient agrees, a formal consent process will take place in clinic and the patient will undergo initial, baseline testing of strength, range of motion, pain scores, and patient reported outcome scores.

Therefore, patients will be either in the nonoperative arm or the operative arm of this study. Within each arm, patients will be randomized via computer to be placed in either the blood flow restriction (BFR) cohort or the traditional (non-BFR cohort). Patients will prospectively undergo rotator cuff rehabilitation using BFR or conventional therapy by physical therapists with extensive experience in rotator cuff rehabilitation who will undergo training on use of BFR.

The nonoperative group will be given identical rehabilitation protocols, with the only difference being the use of a BFR cuff during rehabilitation for the BFR cohort. Similarly, the operative group will be given identical rehabilitation protocols, with the only difference being the use of a BFR cuff during rehabilitation for the BFR cohort.

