Patients undergoing operative rotator cuff repair (RCR) will undergo preoperative rehabilitation prior to surgery for two weeks. Due to limitations of health insurance coverage of physical therapy sessions, the two weeks of preoperative "prehab" will consist of a structured home exercise program that is taught to the patient by a physical therapist during one session and recorded on a physical therapy (PT) diary by the patient during the two weeks leading up to surgery. Patients will be provided with video instruction and training on how to conduct the exercises and this will also be done with and without the use of BFR depending on group allocation (via randomization). Additionally, warning signs for BFR cuff intolerance such as increased pain, swelling, numbness/tingling of the arm will be communicated to the patient. Following surgery patients will immediately be started in a formal physical therapy regimen as an outpatient. Therapy will consist of a structured program progressing from range of motion to strength training and then functional tests. Patients will remain in their allocated BFR or non-BFR group.

Protocol as follows, both groups will use the same protocol with the only difference being use of BFR:

For surgical patients:

- Preop: Patients will undergo a home program consisting of isometric exercises including shoulder extension, abduction, external rotation and internal rotation pushing against a wall.

For both surgical and non-surgical patients:

- Post-op weeks 0-8: Passive shoulder range of motion (ROM) only
- Sling immobilization with active elbow, wrist and hand ROM
- Passive ROM only of shoulder including pendulums, supine elevation in scapular plane, external rotation with arm at side.

8-12 weeks being more active range of motion

- Discontinue sling
- Being active exercises including prone row, standing internal/external rotation with bands, wall slides into shoulder flexion

Weeks 12-20: Strength and function of Side lying shoulder external rotation, increase resistance band exercises

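### The only inclusion sentence shuts out the non-operative arm in which BFR is randomised, and the work deficit behind the 15% endpoint is defined on an operated leg in a shoulder trial

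*Combined protocol and SAP*

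**What the plan says.** **Who is eligible.** Section 2 (Subject Population and Eligibility) gives a single inclusion sentence: "We will include patients aged 18-60 who suffered a rotator cuff tear and are undergoing Rotator Cuff reconstruction". The screening text in the same section says "Subjects will be identified when they present to our ambulatory clinics with RCR tears". It describes how candidates are found and adds no second route to eligibility.

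**Who is to be studied.** Section 1 states the purpose as examining BFR "in patients treated both non operatively and operatively for rotator cuff tears (RCT". Section 3 (Study Procedures) says that treatment follows a "shared decision-making process with the orthopedic surgeon, irrespective of this study", that "patients will be either in the nonoperative arm or the operative arm of this study", and then: "Within each arm, patients will be randomized via computer to be placed in either the blood flow restriction (BFR) cohort" or the conventional one.

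**What happens and when.** Section 3 says "Patients undergoing operative rotator cuff repair (RCR) will undergo preoperative rehabilitation prior to surgery for two weeks". A rehabilitation schedule follows under the heading "For both surgical and non-surgical patients", but its first block is numbered in weeks after surgery. The visit paragraph lists a visit before surgery, a two-week visit labelled as post-operative, a six-week visit and a three-month visit. The last two carry no stated origin.

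**What is measured.** The listed primary outcome is strength by dynamometer. The data-analysis paragraph in section 3 sets the primary endpoint as a 15% difference in total work deficit, obtained by comparing the operated leg with the other leg. Ultrasound measures of the muscle are compared with imaging taken before surgery.

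**The concern.** The eligibility rule and the randomised design describe different populations. A coordinator who applies section 2 as written can enrol nobody into the non-operative arm. One who follows sections 1 and 3 enrols patients who fail the only inclusion criterion.

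The same surgical assumption runs into the outcome definitions. Total work deficit carries both the 15% endpoint and the sample-size statement, yet it is defined on the legs in a shoulder trial and needs an operated limb. The population, the visit timing and the derived outcomes of a whole randomised stratum are therefore not properly specified, and two analysts could construct them differently.

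**Working it through.** **1. Eligibility against design.** The inclusion sentence joins two conditions, a tear and reconstruction, with *and*. A patient managed without surgery fails the second. Nothing else in the plan widens the rule: the chart check in section 2 concerns exclusion criteria only, and the description of arms in section 3 shows intent but is not a criterion. One of the two arms is ineligible as written.

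**2. Which definitions need surgery.**

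| Item (section 3) | Operative patient | Non-operative patient |
|---|---|---|
| Dynamometer strength | Measurable | Measurable |
| Work deficit, operated versus other leg | Wrong limb | Wrong limb, and no operated side |
| Ultrasound change from pre-operative image | Defined | No such image exists |
| Two-week visit | Counted from surgery | No start event |
| Six-week and three-month visits | Origin not stated | Origin not stated |

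Section 3 does give every participant a baseline test at consent, covering strength, range of motion, pain and patient-reported scores. Imaging is not in that list, and the test is not named as week 0 of follow-up.

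**3. The plan's own figure.** The plan states 34 patients (17 per group) for a 15% difference, 80% power and alpha 0.05. It gives no SD, so the figure cannot be reproduced independently. Assuming an SD of 15 percentage points and a two-sided test, the normal approximation gives n = 2 × (1.960 + 0.842)² × (15/15)² = 15.7, rounded up to 16 per group. The t test gives 17 per group, with 80.7% power. Any SD from 14.66 to 15.13 returns 17 by the t test. The figure is attainable but unverified, and this point does not depend on it. What matters here is that the quantity being powered is the work deficit.

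**4. Can the timing gap be sized?** Take three months as 13 weeks.

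- Both arms counted from week 0 of the common schedule: visits at 2, 6 and 13 weeks in each arm. Gap 0.
- Counted from the start of any rehabilitation, including the two weeks before surgery: operative 2 + 2 = 4, 2 + 6 = 8 and 2 + 13 = 15; non-operative 2, 6 and 13. Gap 2 weeks.
- Non-operative visits counted from the baseline test, with a wait *d* before therapy. The documents give no *d*; 0 to 2 weeks is assumed. Time in rehabilitation is 2 − *d*, 6 − *d* and 13 − *d*, so the gap from operative patients is 2 + *d*, or 2 to 4 weeks.

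The answer runs from 0 to 4 weeks, depending on a choice that the plan does not make. No size is claimed.

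**The case against.** The strongest reply is that the intent is plain. Section 1 names both populations, section 3 names both arms and randomises within each, and the study is offered once either treatment plan is in place. On this view the inclusion sentence was simply not updated, and the listed primary outcome can be measured in everyone. That stands as far as it goes. It limits the consequence, but it leaves an eligibility rule that contradicts the design and a derived endpoint on the wrong limb.

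Four stronger readings are tempting, and the documents do not support them:

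- A reader might infer that the non-operative half of the aim cannot be answered. That is too strong, because such patients are likely to be enrolled by intent and their strength can be measured.
- A reader might infer a gap of 2 to 4 weeks in rehabilitation time between same-named visits. That depends on counting from the pre-surgical programme, and at the upper end on an assumed wait. On the common schedule the gap can be 0. It also compares operative with non-operative patients, who are not randomised against each other.
- A reader might infer bias in BFR versus control. Randomisation is within arm, and nothing in the plan shows that unclear timing would differ by allocation.
- A reader might infer low power within each arm. The plan does not say whether 34 applies per arm or overall and gives no SD, so power cannot support this point.

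It is also fair that the missing origin for the six-week and three-month visits affects all patients. The visit paragraph, which mentions wound healing, may describe the surgical pathway only. In that case the non-operative arm lacks a visit list altogether, and its timing is still not fixed.

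**Conclusion.** The point holds as an internal contradiction that is wrong as written. The inclusion sentence excludes one of the two arms. The work deficit names the wrong limb for every patient, and two derived outcomes (work deficit and ultrasound change) are undefined for patients without surgery. Non-operative visit timing is not fixed. The conclusion rests on the wording alone and needs no assumed figure. It does not extend to a lost aim, a bias, a loss of power or a number of weeks.

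Two further inconsistencies touch clinical management and can only be flagged. The common rehabilitation schedule is headed for non-surgical patients but starts from surgery. Separately, the exclusion list in section 2 names a personal history of DVT, while the screening text there and section 4 also mention family history. The surgical wording on consent (section 9) and monitoring (section 12) is a side issue that does not carry the point.

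**What to change.** 1. Amend the inclusion sentence in section 2 to cover rotator cuff tears managed operatively or non-operatively. Alternatively, remove the non-operative arm from sections 1 and 3.
2. Define the work deficit as affected versus unaffected shoulder in all patients. This is needed whichever option is chosen.
3. If the arm stays, state one time origin for its visits and use its baseline assessment as the imaging reference.
4. If the arm stays, the investigators must reconcile the post-surgical week numbering in section 3 with the heading that includes non-surgical patients. Separately, they must reconcile the DVT wording in sections 2 and 4. No clinical rule is proposed here.

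The cost is a wording amendment, and possibly a baseline ultrasound for non-operative patients if none is already taken.

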Throughout this protocol patients will have a pre-operative visit, an early 2 week post operative visit to check range of motion and wound healing, a six week visit to monitor range of motion and potentially clear for active ROM and sling discontinuation, and a three month visit prior to clearance to being return to more aggressive activity. Strength and range of motion will be recorded at each of these visits in order to assess the primary endpoint.

Outcomes:

Primary Outcome:

- Strength to be measured via dynamometer at each clinic visit

Secondary Outcomes:

- Range of motion via goniometer
- Pain via visual analogue scale (VAS) pain scale at each visit
- Patient reported outcomes scores at each visit
- Fatty infiltration and muscle atrophy measured via ultrasound and compared to pre-operative imaging

Plan to recruit patients starting in June 2020. Will enroll patients and collect data from June-2020 to May 2021. Manuscript writing and submission to occur in June 2021.

Data analysis: The primary endpoint of this study was a maximum repetition total work deficit of 15% between the BFR and control group as measured by dynamometer. This was based on previous data showing that a strength deficit of 15% represents a clinically significant difference that is not likely attributable to limb dominance. Work deficit was calculated in each group by comparing the operative leg with the nonoperative leg to obtain a deficit percent. A power analysis was performed before the study to assess the number of patients needed to detect a 15% total work deficit between the BFR and control groups. With a power of 80% (beta level $\frac{1}{4} 0.80$, alpha level $\frac{1}{4} 0.05$), a sample size of 34 (17 patients per group) was obtained. Data will be provided to and analyzed by trained statisticians to determine differences in primary and secondary outcomes.

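### The side-to-side deficit takes the other limb as the normal reference, but the entry criteria do not exclude known disease, symptoms or past surgery of the contralateral shoulder

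*Combined protocol and SAP*

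**What the plan says.** **Endpoint (Section 3, Data analysis).** The protocol states: "The primary endpoint of this study was a maximum repetition total work deficit of 15% between the BFR and control group as measured by dynamometer". The deficit is a within-patient comparison of the two limbs: "Work deficit was calculated in each group by comparing the operative leg with the nonoperative leg to obtain a deficit percent". The wording refers to legs in a shoulder trial. That needs its own correction, but the point below is the same once it reads shoulder.

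**Reason for 15%.** The figure is supported by data said to show that "a strength deficit of 15% represents a clinically significant difference that is not likely attributable to limb dominance". This is a side-to-side argument: dominance is taken to be the only ordinary reason for the two limbs to differ.

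**Entry criteria (Section 2).** Inclusion reads: "We will include patients aged 18-60 who suffered a rotator cuff tear and are undergoing Rotator Cuff reconstruction". Exclusion reads: "Subjects will be excluded if they are undergoing revision RCR reconstruction, history of DVT, neurovascular injury, unable to tolerate BFR treatment", followed by "unable to complete physical therapy and peripheral vascular disease". Screening is by detailed history, chart review and a set of questions aimed mainly at DVT.

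**Randomisation and analysis (Section 3).** Patients are randomised by computer within the operative and nonoperative arms. Continuous outcomes are compared by two-group t tests, and a regression considers demographic confounders. The state of the other shoulder appears in none of these.

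**The concern.** A side-to-side deficit measures the treated shoulder only to the extent that the other shoulder is a sound yardstick. Nothing in Section 2 secures that. Revision repair describes the operation now being done. Neurovascular injury names no side and does not cover cuff disease. A patient with a known tear, current symptoms or a past repair on the other side is therefore eligible.

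If that shoulder is weak, the denominator is low and the deficit comes out too small, zero or negative. The outcome is then on a different scale for that patient. With 17 per group and a nominal 80% power, a handful of such patients can widen the spread of the primary outcome, and an uneven split of them can move the group contrast by chance.

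**Working it through.** **1. Inputs from the protocol.** Target difference 15 points, power 80%, alpha 0.05, 17 per group (34 in total), two-group t test; all from Section 3. No SD is given, and sidedness is not stated (two-sided taken here).

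**2. The plan's own figure.** Without an SD, 17 per group cannot be reproduced directly, so I solved for the SD that it implies. By the normal approximation, SD = 15 × √(17/2) / (1.960 + 0.842) = 15.6. By the noncentral t distribution it is 15.1. I use SD = 15 below. At that value the t test has 80.7% power with 17 per group and 78.1% with 16, so 17 is the smallest group size that reaches 80%.

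**3. Effect of the other shoulder on one patient's deficit.** Deficit = 100 × (1 − affected / other). Hold the affected side at 60 units (assumed):

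| Other side | Deficit | Shift from the healthy case |
|---|---|---|
| 100 (healthy) | 40.0% | none |
| 90 | 33.3% | about 7 points |
| 80 | 25.0% | 15 points |
| 70 | 14.3% | about 26 points |
| 60 | 0% | 40 points |
| 50 | −20% | 60 points |

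The treated shoulder is the same in every row.

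**4. Effect on SD and power.** Suppose a share p of patients has its deficit shifted by s points. Then SD = √(15² + p(1 − p)s²). For p = 0.1 and s = 26 this is √(225 + 0.09 × 676) = 16.9. Power is for a 15-point difference, 17 per group, two-sided t test. The shares are assumptions, as the documents give none.

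| Shift | p = 10% | p = 20% | p = 30% |
|---|---|---|---|
| None | 81% | 81% | 81% |
| 7 points | 80% (SD 15.1) | 79% (SD 15.3) | 79% (SD 15.3) |
| 15 points | 77% (SD 15.7) | 75% (SD 16.2) | 73% (SD 16.5) |
| 26 points | 71% (SD 16.9) | 64% (SD 18.3) | 60% (SD 19.2) |

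**5. A second model.** Let true affected-side strength average 70% of normal in one group and 85% in the other, with SD 15.15, and let a weak denominator also rescale the treatment difference. Power then falls from 80% to 65%, 58% or 54% with the other shoulder at 70% of normal, and to 74%, 71% or 69% with it at 80%. The direction is the same; the size depends on the model.

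**6. Chance imbalance.** If each patient independently has probability 10%, 20% or 30% of being affected, the two groups of 17 differ by three or more such patients with probability 15%, 28% or 35%. An excess of three shifts the difference in means by 3 × 26 / 17 = 4.6 points, 3 × 15 / 17 = 2.6 points or 3 × 7 / 17 = 1.2 points, against a target of 15.

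**The case against.** **The endpoint may not be a deficit at all.** The outcome list in Section 3 gives only "Strength to be measured via dynamometer at each clinic visit", with no reference limb, and the hypothesis in Section 1 is about strength gains. If the sponsor settles on affected-side strength, this point falls away. That is true. But the deficit is what the protocol names as the primary endpoint and sizes the trial on, so as written the point stands.

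**Patients misclassified as recovered.** A reader might infer that a patient with two weak shoulders would be counted as recovered, or would pass a 15% cut-off. The documents do not support this. They define no recovered or responder category. The 15% serves as the between-group difference to detect, and continuous outcomes go to a t test.

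**Bias toward one group.** A reader might also infer that the comparison is biased, or that the index no longer responds to treatment. Neither follows. Randomisation balances contralateral disease in expectation, and a stronger treated shoulder still gives a smaller deficit against a weak reference. The index is rescaled, not blind to treatment.

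**The power loss is assumed.** This objection stands. The SD is back-solved, and the share and severity are not in the documents. Symptoms or past surgery need not mean weakness. If the data behind the sample size already came from people with unselected other limbs, some of the extra variance is counted twice. With a mild shift, almost nothing is lost.

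**Conclusion.** The point holds in a limited form. The protocol uses the other limb as the normal reference for its primary deficit, and no entry criterion, stratification or adjustment protects that reference. Patients admitted under the plan can therefore have a mis-scaled primary outcome.

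The consequence is lost precision and exposure to chance imbalance, not systematic bias. Under the simple mixture in the working, power lies anywhere from about 80% (7-point shift) to 60% (26-point shift in 30% of patients), against about 81% with no such patients. The second model reaches 54% at its worst. These figures illustrate a range and are not estimates for this trial. The gap in the criteria is certain from the text; its size is not. Since the remedy is cheap and the sample size leaves no margin, the change should be made.

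**What to change.** 1. In Section 2, add to the exclusions: known rotator cuff tear, current symptoms or previous surgery of the contralateral shoulder. Ask about these in the detailed history already taken at screening.
2. In Section 3 (Data analysis), add a sensitivity analysis in all randomised patients, not only those with a contralateral problem: repeat the primary comparison with affected-side strength, adjusted for its baseline value, in place of the deficit. This does not depend on the other limb. It also covers patients already enrolled and silent contralateral disease that a history would miss.

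**Cost.** One exclusion line, one screening question and one extra model. No new measurement is needed, because Section 3 already has strength tested at baseline and at each visit. The downside is a somewhat smaller eligible pool, which matters in a trial of 34.
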